9.2. Clinical Laboratory Evaluations

Clinical laboratory tests (including hematology, clinical chemistry, coagulation, urinalysis, hepatitis serology, thyroid function, and pregnancy test) will be collected per the timing presented according to the protocol. Clinical laboratory values will be graded according to NCI CTCAE for applicable tests. International System of Units (SI) will be used in the summaries.

All laboratory data will be presented in listings by patient and visit for each panel.

9.2.1. Hematology

The hematology tests will include hemoglobin, hematocrit, white blood cell, neutrophils, bands, lymphocytes, monocytes, eosinophils, basophils, and platelets.

Descriptive statistics of observed and change from baseline values for hematology tests will be presented at the scheduled visits and for the overall worst value post-baseline. A shift table representing the change from the baseline grade to the worst post-baseline grade will also be provided. The number and percentage of patients with at least a 2-grade increase from baseline will be summarized treatment arm and dose cohort for Phase I and Phase II, and total for each treatment arm combining Phase I and Phase II.

A listing for hematology tests will be provided by patient and visit.

9.2.2. Clinical Chemistry

The clinical chemistry tests will include magnesium, bicarbonate, sodium, potassium, phosphorus, chloride, calcium (corrected), alkaline phosphatase, alanine aminotransferase (ALT), aspartate aminotransferase (AST), lactate dehydrogenase (LDH), total bilirubin, glucose, total protein, albumin, creatinine, blood urea nitrogen (BUN), uric acid, lipase, and amylase and thyroid-stimulating hormone.

Descriptive statistics of observed and change from baseline values for clinical chemistry tests will be presented at the scheduled visits and for the overall worst value post-baseline. A shift table representing the change from the baseline grade to the worst post-baseline grade will also be provided. The number and percentage of patients with at least a 2-grade increase from baseline will be summarized.

A listing for clinical chemistry tests will be provided by patient and visit.

9.2.3. Coagulation

The coagulation tests will include prothrombin time, partial thromboplastin time, and fibrinogen.

Descriptive statistics of observed and change from baseline values for coagulation tests will be presented at the scheduled visits and for the overall worst value post-baseline. A shift table representing the change from the baseline grade to the worst post-baseline grade will also be provided.

A listing for coagulation tests will be provided by patient and visit.

9.2.4. Urinalysis

A listing for urinalysis will be provided by patient and visit.

9.2.5. Hepatitis Serology

A listing for hepatitis serology will be provided by patient at screening.

9.2.6. Pregnancy Testing

A listing for pregnancy test will be provided by patient and visit.

9.3. Vital Signs

Vital sign measurements include pulse (beats per minute), systolic blood pressure (mmHg), diastolic blood pressure (mmHg), temperature (°C), and weight (kg). Descriptive statistics will be provided for observed values and change from baseline values at the scheduled visits.

Patients with abnormal post-baseline vital sign values, identified by values outside the threshold values defined below, will be summarized by visit, treatment arm and dose cohort for Phase I and Phase II, and total for each treatment arm combining Phase I and Phase II.

Vital Signs	Abnormality
Pulse	<45 beats per minute or >90 beats per minute
Systolic blood pressure	<90 mmHg or >140 mmHg
Diastolic blood pressure	<40 mmHg or >90 mmHg
Temperature	<36.5°C or >37.3°C

All vital signs will be presented in a listing.

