In the rat and monkey, ATA analysis indicated a dose-dependent increase in antibodies (IgM and IgG) directed against human OX40L on Day 29 in all groups dosed with mRNA-2416. Since all animals treated with mRNA-2416 developed anti-hOX40L response (and homology of cyno and human OX40L is considered high = 99%), seroconversion may occur in patients. Published studies in knock-out animals have indicated that there is no or only minor contribution of this protein to immunity since it is part of a redundant signaling system ([Boettler et al 2012](#), [Kopf et al 1999](#), [Murata et al 2000](#), [Salek-Ardakani et al 2008](#)). Therefore, seroconversion in patients is not anticipated to cause significant risk.

The safety of mRNA-2416 was evaluated in an in vivo genotoxicity study in Sprague Dawley rats using the bone marrow micronucleus test. In addition, the concentrations of mRNA-2416 in the plasma were determined. Refer to the Investigator's Brochure for study details.

Results showed mRNA-2416 induced chromosome damage in rat bone marrow immature erythrocytes, when administered intravenously at up to 2 and 3 mg/kg, the estimated maximum tolerated doses for male and female Sprague Dawley rats, respectively. These results were considered weakly positive. Based on the relative lack of response in females at the higher dose (3 mg/kg), the mild nature of response (< 3-fold), the high doses administered by the IV route, and the lack of in vitro response of SM-86, the risk of genotoxicity in patients is considered low.

The safety of SM-86, a novel lipid excipient of the mRNA-2416, was evaluated in 2 in vitro genotoxicity studies. SM-86 did not show any evidence of genotoxic activity in either assay.

This study represents the first-in-human clinical study for mRNA-2416. As of 08-Feb-2019, 32 patients with advanced relapsed/refractory malignancies have been enrolled. General adverse reactions, reported in 3 or more subjects, included site pain, injection site reaction (erythema, edema, itching), pyrexia, flushing, fatigue, chills, and nausea with all the events being mild to moderate in severity except for one Grade 3 injection-related reaction. Refer to the current mRNA-2416 and durvalumab investigator's brochures (IB) for a complete summary of pre-clinical and clinical information.

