13.4.2 SAFETY ANALYSES

All safety analyses will be conducted in the Safety Population.

Verbatim descriptions of AEs will be coded using Medical Dictionary for Regulatory Activities (MedDRA). Summary tables will be provided for all TEAEs. A TEAE is defined as any AE that newly appeared, increased in frequency, or worsened in severity following initiation of study drug. The number and percentage of patients reporting a TEAE in each dose cohort will be tabulated by system organ class and preferred term, severity, and relationship to study drug. The number and percentage of patients reporting a SAE and reporting a TEAE leading to premature discontinuation of study drug in dose cohort will be summarized by system organ class and preferred term. For all analyses of TEAEs, if the same AE (based on preferred term) is reported for the same patient more than once, the AE is counted only once for that preferred term and at the highest severity and strongest relationship to study drug. Clinically relevant abnormal physical examination results are recorded as AEs; thus, physical examination data will not be summarized in a table.

Descriptive statistics for hematology, chemistry, and coagulation data will be summarized by dose cohort and time point and for the overall worst value post-baseline. Toxicity grades will be determined based on the CTCAE criteria version 4.03, and shift tables will be presented. The number and percentage of patients with at least a 2-grade increase from baseline will be summarized by dose cohort.

Descriptive statistics of the change from baseline for vital signs will be summarized by dose cohort and time point. Abnormal values, identified by threshold values defined in the SAP, will be summarized.

Descriptive statistics for ECG parameters at baseline and at the Post-treatment Safety Assessment visit and the change from baseline will be presented by dose cohort.

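### The SAP's abnormal vital-sign table ignores baseline and uses a narrow temperature band, so its temperature counts are weakly specific and could mislead if low and high values are pooled

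*SAP*

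**What the plan says.** Protocol 13.4.2 leaves the limits to the SAP: "Abnormal values, identified by threshold values defined in the SAP, will be summarized". SAP 9.3 then sets them and makes the flag depend only on the post-baseline value: "Patients with abnormal post-baseline vital sign values, identified by values outside the threshold values defined below, will be summarized by visit", broken down by arm and dose cohort. The limits are:

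- temperature "<36.5°C or >37.3°C"
- pulse "<45 beats per minute or >90 beats per minute"
- systolic pressure "<90 mmHg or >140 mmHg"
- diastolic pressure "<40 mmHg or >90 mmHg"

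Each sign has a low and a high limit. The section does not say whether the two directions get separate rows.

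The same section also plans a companion summary: "Descriptive statistics will be provided for observed values and change from baseline values at the scheduled visits". All vital signs are listed.

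Laboratory data are handled differently. SAP 9.2.1 to 9.2.3 give hematology, chemistry and coagulation a table of baseline grade against worst post-baseline grade. Hematology and chemistry also get a count of patients rising by at least two grades. SAP Section 4 defines baseline as the last assessment before first dose, and the Schedule of Events collects vital signs at screening and on Day 1.

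**The concern.** A threshold table is meant to pick out the few patients whose values moved to a worrying level, which a mean change in a small cohort can hide. Three features work against that here.

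- **No baseline condition.** A patient with systolic pressure of 145 mmHg before and after dosing is counted as abnormal. Eligibility excludes only medically uncontrolled hypertension (Protocol 9.2, criterion 13a), so such patients can enter.
- **A narrow temperature band.** Ordinary readings just below 36.5 °C are flagged.
- **Direction not specified.** If low and high share one count, a reading of 36.4 °C and a fever weigh the same. A patient who moves from 36.4 to 38.5 °C leaves the count unchanged.

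Temperature is where discrimination matters most. The reactions already seen with mRNA-2416 include "pyrexia, flushing, fatigue, chills, and nausea" (Protocol 6.2).

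**Working it through.** The plan states no expected abnormality rate, so there is no figure of its own to reproduce. The limits come from SAP 9.3. All means, SDs and correlations below are assumptions, because the documents give none.

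**Flag rate at one visit, no drug effect.** For a normal value with mean m and SD s, the rate is Φ((L − m)/s) + 1 − Φ((U − m)/s), where L and U are the lower and upper limits.

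- Temperature, m = 36.6, s = 0.4: low Φ(−0.25) = 0.401; high 1 − Φ(1.75) = 0.040; total 0.441.
- Lowest case in the assumed range, m = 36.9, s = 0.3: 2 × Φ(−1.33) = 0.18.
- Highest case, m = 36.4, s = 0.3: Φ(0.33) + 1 − Φ(3.00) = 0.63.
- Pulse, m = 80, s = 12: about 20%. Over means 70 to 85 and SDs 10 to 14: about 3% to 36%.
- Systolic, m = 127, s = 16: about 22%. Over means 120 to 130 and SDs 14 to 18: 9% to 30%.
- Diastolic, m = 75, s = 10: about 7%. Over means 72 to 78 and SDs 9 to 11: 2% to 14%.

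**What a true temperature rise does to the count** (m = 36.6, s = 0.4):

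| True rise | Low | High | Low and high pooled |
|---|---|---|---|
| none | 40% | 4% | 44% |
| +0.3 °C | 16% | 16% | 32% |
| +0.5 °C | 7% | 31% | 38% |
| +1.0 °C | 0.3% | 77% | 78% |

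The high side alone rises steadily. The pooled count falls first and then recovers.

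The reason is geometric. The midpoint of the band is (36.5 + 37.3)/2 = 36.9 °C. For any symmetric distribution with mean m below 36.9, a shift of 2 × (36.9 − m) mirrors it across the midpoint and leaves the pooled rate unchanged, whatever the SD. At m = 36.6 that shift is 0.6 °C; at m = 36.5 it is 0.8 °C. At m = 36.8 it is only 0.2 °C, and with s = 0.3 a rise of 0.3 °C takes the pooled rate up from 21% to 28%. The masking therefore depends on a usual mean clearly below 36.9 °C.

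**Pulse is not masked.** At m = 80, s = 12, a rise of 10 bpm puts the mean at the upper limit, so the flag rate goes from 20% to 50%.

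**Effect of a baseline condition.** This was simulated with no drug effect and within-patient correlation 0.5, at the central means and SDs above. Only patients inside the limits at baseline were counted, as a share of all patients at a visit:

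| Sign | Value alone | Newly outside |
|---|---|---|
| Temperature | 44% | 19% |
| Pulse | 20% | 11% |
| Systolic | 22% | 13% |
| Diastolic | 7% | 5% |

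For temperature, 0.19/(1 − 0.44) is about one third of those normal at baseline. A baseline condition roughly halves the noise, but temperature stays high while the limits stay as they are.

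**The case against.** The strongest reply is that this table does not stand alone. SAP 9.3 also gives change from baseline at each visit, and every value is listed. Injection reactions must be recorded as adverse events (Protocol 10.1), and SAP 9.1 tabulates those by preferred term, grade and relationship. The Schedule of Events takes dosing-day vital signs pre-dose and as clinically indicated, so apart from Cycle 1 Day 2 a by-visit table would mostly miss acute fever under any limits. All of this stands, and it keeps the point minor. It does not repair the table itself.

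Four stronger readings are tempting but not supported:

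- **Most patients will count as abnormal.** The planned table is by visit and by sign. At a visit, temperature passes 50% only under some assumptions, and the other signs stay at or below about 36%. Very high figures, such as 99% for temperature in the central case, describe patients ever flagged over 16 visits. The SAP plans no such count, and no any-sign composite.
- **The table cannot show a safety signal.** The pulse result contradicts this, as does a temperature rise of 1.0 °C (44% to 78%, even pooled).
- **Every small dose cohort will look highly abnormal.** At 18% flagged, a cohort of three has no flagged temperature with probability 0.82³ = 0.55; at 44%, 0.56³ = 0.18.
- **Low and high are pooled.** The SAP does not say so. It only fails to say that they are separated.

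**Conclusion.** The point holds as a minor defect in a descriptive safety table. The rule ignores baseline for every sign, although the SAP defines baseline and uses it for laboratory shift tables. The temperature table is weakly specific: about 18% to 63% of unaffected patients are flagged at a visit, mostly on the low side when the mean is below 36.9 °C. It can also move the wrong way if directions are pooled. Pulse above 90 is weakly specific only. For blood pressure, the issue is confined to patients already outside the limits at baseline.

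The direction of these conclusions follows from the rule and the limits. Their size rests on the assumed distributions, and the masking also needs pooling and a mean below 36.9 °C. No primary analysis is affected. This is a cheap improvement.

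**What to change.** In SAP 9.3:

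1. Tabulate values below the lower limit and above the upper limit separately for each sign.
2. Count patients newly outside a limit relative to baseline, applied by direction, so that a patient low at baseline who becomes high is still counted as newly high. Alternatively, add a table of baseline category against worst post-baseline category, as SAP 9.2 does for laboratory data.
3. Revise or justify the temperature flag limits. The CTCAE v4.03 grading that the study already uses is one option; the documents do not reproduce its temperature boundaries, so the SAP would need to state them. The >38.3 °C figure in Protocol 8.4.2 should not be imported, because it belongs to an Arm B dose-limiting toxicity criterion for neutropenia with fever and is not a general vital-sign limit.

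The cost is SAP wording and a little table programming on data already collected. The downside is that small changes would then appear only in the change-from-baseline summaries and the listings.

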9.4. Electrocardiogram

Twelve-lead ECG assessments include ECG heart rate (beats per minute), PR interval (milliseconds), QRS duration (milliseconds), QT interval (milliseconds), and RR interval (milliseconds). Descriptive statistics will be provided for observed values and change from baseline values at the scheduled visits.

The number and percentage of patients with each ECG overall interpretation will be summarized at scheduled visits.

All ECG assessments will be presented in a listing.

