3 SCHEDULE OF EVENTS

Study Procedure	Screening	Cycle 1				Cycle 2 - Cycle 6		End of Treatment	Follow-up	
Study Days	-14 to -1	1	2	8	15	1	15	Within 14 days of Treatment Discontinuation	30 and 90 Day Safety F/U	90 and 180 Day Disease Progression F/U Period
Visit Window	-	-	+1 day		±2 days	±2 days		±2 days	-2/+7 days	±30 days
Clinical Assessments										
Informed Consent	X									
Inclusion/exclusion criteria	X									
Demographics ¹	X									
Medical/Surgical/Cancer Histories ²	X									
Vital Signs ³	X	X	X	X	X	X	X	X	X	
Height	X									
Body Weight	X	X				X		X	X	
Physical Exam ⁴	X							X		
Symptom-directed Physical Exam		X	X	X	X	X	X		X	
ECOG Performance Status	X					X		X	X	
Concomitant Medications ⁵	X	X	X	X	X	X	X	X	X	
Adverse Events	X	X	X	X	X	X	X	X	X	X
Clinical Laboratory Assessments										
Full Blood Count ⁶	X	X	X	X	X	X	X	X	X	
Coagulation ⁶	X	X				X				
Serum Chemistry Panel ⁶	X	X	X	X	X	X	X	X	X	
Thyroid Function ¹²	X	X			X	X		X	X	
Urinalysis ⁶	X							X		
Pregnancy Test ¹⁰	X	X				X		X	X	
12-Lead Electrocardiogram	X							X	X	
HIV, Hepatitis B & C Tests ^{6,11}	X									
Study Drug Administration										

Study Procedure	Screening	Cycle 1				Cycle 2 - Cycle 6		End of Treatment	Follow-up	
Study Days	-14 to -1	1	2	8	15	1	15	Within 14 days of Treatment Discontinuation	30 and 90 Day Safety F/U	90 and 180 Day Disease Progression F/U Period
Visit Window	-	-	+1 day	±2 days		±2 days	±2 days	-2/+7 days	±30 days	
mRNA-2416 intratumoral injection ⁷		X			X	X	X ⁷			
Durvalumab infusion		X				X				
Tumor Assessments										
Tumor assessment ⁸	X					C3 & C5		X		X
PK/Pharmacodynamic Assessments										
PK Sampling ⁹		X	X	X		C2				
Cytokine Profile Sampling ⁹		X	X	X		C2				
Serum Immunogenicity Sample ⁹		X			X	X	C3 & C6	X		
Tumor Biopsy	X	Refer to Section 10.5								

1. Demographics include age, sex, race, and ethnicity.
2. Prior cancer history includes (i) date of diagnosis, (ii) staging, (iii) all previous therapies (ie, chemotherapy, immunotherapy, biologic or targeted agents, experimental therapies, radiotherapy, and surgery), (iv) previous therapy details (ie, regimen, start and stop dates), and (v) best response for each regimen.
3. Vital signs include temperature, blood pressure, preferably in seated position, and pulse rate. Pre-dose and as clinically indicated before every infusion or administration.

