9. Receipt of live attenuated vaccine within 30 days prior to the first dose of study treatment. Note: Patients, if enrolled, should not receive live vaccine whilst receiving study treatment and up to 30 days after the last dose of study treatment.
10. History of human immunodeficiency virus infection
11. Active/chronic hepatitis B or C
12. Major surgical procedures ≤ 28 days or non-study-related minor procedures ≤ 7 days prior to C1D1. In all cases, the patient must be sufficiently recovered and stable before treatment administration.
13. Any of the following cardiac abnormalities:
 - a. Medically uncontrolled hypertension
 - b. New York Heart Association Class III or IV cardiac disease
 - c. Myocardial infarction within prior 6 months
 - d. Unstable angina
 - e. Unstable arrhythmias or mean QT interval corrected for heart rate using Fridericia's formula (QTcF) ≥ 470 ms calculated from 3 ECGs (within 15 minutes at 5 minutes apart)
14. History of another primary malignancy except for:
 - Malignancy treated with curative intent and with no known active disease ≥ 5 years before the first dose of IP and of low potential risk for recurrence

- Adequately treated non-melanoma skin cancer or lentigo maligna without evidence of disease
- Adequately treated carcinoma in situ without evidence of disease

15. Patients requiring active systemic anticoagulation at the time of intratumoral injection or biopsy

16. Active GI bleeding

17. Females who are pregnant or breastfeeding

18. Any other unstable or clinically significant concurrent medical condition (eg, substance abuse, psychiatric illness/social situations, uncontrolled intercurrent illness including active infection, arterial thrombosis, symptomatic pulmonary embolism, active interstitial lung disease, serious chronic gastrointestinal conditions associated with diarrhea, etc.) that would, in the opinion of the investigator, jeopardize the safety of a patient, impact their expected survival through the end of the study participation, and/or impact their ability to give written informed consent or comply with the protocol.

19. For patients who have received prior anti-PD-1 or anti PD-L1 therapy, a patient must not have experienced any of the following:

- a. Must not have experienced a toxicity that led to permanent discontinuation of prior immunotherapy.
- b. All AEs while receiving prior immunotherapy must have completely resolved or resolved to baseline prior to screening for this study.

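### SAP 9.4 summarises uncorrected QT only and never derives QTcF, so a heart-rate difference between visits can mask or mimic a QT change

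*SAP*

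**What the plan says.** SAP 9.4 names five ECG parameters: heart rate, PR, QRS, "QT interval (milliseconds), and RR interval (milliseconds". For these, "Descriptive statistics will be provided for observed values and change from baseline values at the scheduled visits". The only other summary is categorical: "The number and percentage of patients with each ECG overall interpretation will be summarized at scheduled visits". All ECGs are also listed. The section gives no correction formula and no numeric abnormality limit, whereas SAP 9.3 sets such limits for vital signs.

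The protocol uses a corrected interval at entry. Exclusion criterion 13e (Section 9.2, repeated in the synopsis) refers to the "mean QT interval corrected for heart rate using Fridericia's formula", with a limit of "470 ms calculated from 3 ECGs".

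Protocol 13.4.2 does not supply the correction for the analysis: "Descriptive statistics for ECG parameters at baseline and at the Post-treatment Safety Assessment visit and the change from baseline will be presented by dose cohort". It does not say which parameters. SAP Section 1 states that the SAP prevails where methods differ, and SAP Section 13 records no ECG-related change.

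In the Schedule of Events (protocol Section 3), the row "12-Lead Electrocardiogram" is marked at Screening, End of Treatment and the 30- and 90-day safety follow-up, and nowhere else.

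**The concern.** Raw QT shortens as heart rate rises and lengthens as it falls. A change from baseline in raw QT therefore reflects both the heart rate at the two visits and any change in repolarisation, and the table cannot separate them. The error can run either way: a real lengthening may be hidden, or an apparent one created by rate alone.

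The trial also selects patients on one QT measure and reports another. The reported values cannot be read against the measure used to decide eligibility. The ECG is a named safety parameter (protocol 7.7), and safety is a Phase I primary objective, so a table that can be misread in both directions is worth correcting when the data for the correction are already collected.

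**Working it through.** The documents contain no ECG figure to reproduce. The check has two parts: what the text provides, and how large the effect could be.

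**Text.** QT and RR are in SAP 9.4. QTcF and Fridericia appear only in exclusion criterion 13e. No corrected QT is derived in the SAP.

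**Formula.** QTcF = QT / (RR in seconds)^(1/3), with RR = 60 / heart rate. SAP 9.4 gives RR in milliseconds, so it is divided by 1000 first.

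**Assumed inputs.** QT 400 ms and heart rates of 50 to 100 bpm. These are illustrations, not trial data.

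*Masking: heart rate 70 to 90 bpm, QT fixed at 400 ms.*
- At 70 bpm: RR = 0.857 s and QTcF = 400 / 0.857^(1/3) = 421.1 ms.
- At 90 bpm: RR = 0.667 s and QTcF = 400 / 0.667^(1/3) = 457.9 ms.
- Raw QT change = 0. QTcF change = 457.9 − 421.1 = 36.8 ms.

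*Mimicking: heart rate 70 to 55 bpm, QTcF fixed at 421.1 ms.*
- At 55 bpm: RR = 1.091 s and QT = 421.1 × 1.091^(1/3) = 433.5 ms.
- Raw QT change = 433.5 − 400 = 33.5 ms. QTcF change = 0.

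*Range.* The third column holds QT at 400 ms. The fourth is the QTcF difference from 70 bpm, which the raw table would show as zero. The last is the raw QT equivalent to a QTcF of 470 ms.

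| Heart rate (bpm) | RR (ms) | QTcF at QT 400 (ms) | Difference from 70 bpm (ms) | QT equal to QTcF 470 (ms) |
|---|---|---|---|---|
| 50 | 1200 | 376.4 | −44.7 | 499.4 |
| 60 | 1000 | 400.0 | −21.1 | 470.0 |
| 70 | 857 | 421.1 | 0 | 446.5 |
| 80 | 750 | 440.3 | +19.2 | 427.0 |
| 90 | 667 | 457.9 | +36.8 | 410.6 |
| 100 | 600 | 474.3 | +53.2 | 396.4 |

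A shift of 10 bpm from 70 thus moves QTcF by about 20 ms at constant QT. The raw QT that corresponds to 470 ms runs from about 396 to 499 ms over this range, so no single raw value stands in for the protocol's limit. The 100 bpm row is an extreme case: SAP 9.3 already flags a pulse above 90.

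**The case against.** **Other outputs give partial cover.** Heart rate and RR are summarised, overall interpretations are counted and every ECG is listed. Protocol 12.4 has clinically significant abnormal findings reported as adverse events. This limits what is lost. It does not replace the correction, which is made within each ECG and cannot be recovered from separate summaries of QT and RR. The interpretation counts give no magnitude and no stated QTcF criterion. A derivation from the listings would be possible but not pre-specified.

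**The parameter list may not be exhaustive.** That reading is possible, but with no derivation in the SAP, a programmer following it would produce no QTcF.

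**The ECG schedule limits the value of any QT summary.** This stands. A reader might infer that the pyrexia, chills and flushing reported in protocol 6.2 make on-treatment heart-rate change likely and so distort the table. The documents do not support that. No ECG is scheduled on a dosing day or during Cycles 1 to 6, and protocol 10.1 describes monitoring for injection reactions over hours to a day or two. Nothing suggests that those reactions are present at the scheduled ECGs. The point needs only that heart rate can differ between screening and a later visit.

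**The 470 ms limit is not an on-study threshold.** This also stands. It is an entry criterion on the mean of three ECGs taken within 15 minutes. The documents do not require replicates after baseline, so applying the limit to single later readings would not compare like with like.

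**Conclusion.** The point holds. The SAP analyses change in uncorrected QT although the inputs for Fridericia's correction are collected and the protocol relies on that correction at entry. With the assumed values, moderate heart-rate differences produce a discrepancy of roughly 20 to 37 ms in either direction. The actual size depends on how heart rate differs between visits, which the documents do not show.

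A reader might go further and conclude that the missing correction is what stops the ECG table from showing whether the regimen prolongs QT. The documents do not support that. With ECGs only at Screening, End of Treatment and safety follow-up, a QTcF table could not show acute post-dose effects either. The correction would make the scheduled comparisons interpretable and no more.

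The weight is low. This is a descriptive safety table, and no primary efficacy result, error rate or sample size depends on it. Whether the case report form already records QTcF cannot be seen from these documents.

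**What to change.** In SAP 9.4:

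1. Derive QTcF = QT / (RR in seconds)^(1/3) for each ECG and summarise the value and its change from baseline at the scheduled visits, alongside the existing parameters.
2. State that the mean of the screening replicates is the ECG baseline. SAP Section 4 defines baseline as the last assessment before first dose, which does not say how three readings combine. State also whether post-baseline ECGs are single or replicate.
3. Add a pre-specified categorical count of patients by QTcF. If 470 ms is one of the cut-points, note that it is an entry limit defined on a mean of three ECGs.
4. Add a sentence saying that the ECG schedule does not permit assessment of acute post-dose effects.

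The cost is a few lines of programming on data already collected, plus the decision on replicates. Study conduct does not change.
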